For those at high risk, the following will be considered based on clinical judgment:

- Referral to a high risk treatment program
- Emergency room (voluntary)
- Emergency room (involuntary)

HAM-D 17 Scores between 15-25 at the eligibility assessment will prompt a clinical evaluation to address whether or not the patient is sufficiently stable to delay treatment for depression in order to participate in the study. If it is determined by the clinician that it would not be appropriate for the patient to participate in the study due to elevated levels of distress that warrant more immediate attention, the patient will be referred for empirically-validated treatment for depression within the Columbia Veterans Research Center (IRB #7218) (e.g. SSRI). Patients who are referred for immediate treatment may be offered the opportunity to be re-evaluated for study participation at a later date as warranted.

Trauma-Focused Equine-Assisted Therapy: (1) Therapists experienced in treating PTSD patients will assess this distress continually as part of treatment and will ask for additional evaluations or PI intervention when clinically appropriate. Every effort will be made to insure patients' comfort during treatment, and patients will be withdrawn if needed. (2) Risk will be minimized in two ways: first, through careful monitoring and handling of horse behavior during treatment sessions by trained horse handlers and assistants. Second, horses will not be ridden at any point during the treatment, horse riding carries a greater risk of injury than interacting with horses on the ground.

Videotaping: The purpose of the videotaping will be explained, confidentiality will be respected, and tapes will be erased after the spot checks or following supervision. Informed consent for taping will be obtained.

Audiotaping: The purpose of the audiotaping will be explained, confidentiality will be respected, and tapes will be erased after the spot checks or following supervision. Informed consent for taping will be obtained.

MRI Scanning: Patients participating in the MRI scans will be screened by interview and questionnaire to determine the presence or absence of metallic objects, and informed that they cannot participate in the study if their body contains any paramagnetic metal other than standard dental work. Staff will be available for help and support if the subject feels anxious or claustrophobic in the MRI scanner and can stop the scan at the subject's request. To reduce noise discomfort earplugs will be provided.

Other Procedures for Minimizing Risk:

- 1) Careful medical and psychiatric screening to identify patients for whom risk for potential adverse effects are elevated. Such patients will be excluded from the study. In such cases clinicians will follow the protocol for minimizing risks during interviews and assessments described above.
- 2) Patients with any of the following will be removed from research and treated openly or as clinically indicated: a) the occurrence of assaultive or illegal behavior; b) the occurrence of active suicidal ideation at any point during the trial as assessed by clinical interview; c) behaviors while intoxicated that are a danger to self or others.
- 3) Inclusion of psychoeducation about PTSD, the treatment process and memory triggers within the therapeutic framework.

- 4) Careful monitoring of patients during pretreatment and study participation by experienced clinicians. Patients will see the same clinicians for each of their treatment visits.
- 6) Ability to remove any patient from the study who evidences significant clinical deterioration during treatment. Provisions will be made for appropriate clinical care of such patients at the Columbia Veterans Research Center (IRB #7218).
- 7) Patients failing to benefit from the study treatment will be discharged from the study and provided with appropriate clinical care based on weekly review with termination criteria
- 8) All data will be coded and stored in locked files to insure confidentiality.

Methods to Protect Confidentiality

Describe methods to protect confidentiality

All data collected (including audio-and videotape data) will be kept confidential and used for research purposes only. Patient charts will be kept in locked file cabinets identified by number rather than by name. Access to research records is restricted to research staff and Federal, State, and Institutional regulatory authorities. Electronic data will be protected by password access. No names of subjects will be recorded on any audio or video-recordings or written in any research instrument or tape. No subject's identifying data will be published. Audio and video recordings will be stored for up to three years after which time they will be erased and properly destroyed.

Will the study be conducted under a certificate of confidentiality?

No

Direct Benefits to Subjects

Direct Benefits to Subjects

All participants will receive a complete psychiatric evaluation, results of which will be communicated to the participants and their physician, at the participant's request. PTSD symptoms may improve as a result of the EAT treatment. Participants will receive no direct benefits from the fMRI scans.

A potential benefit to society of this research is that the knowledge gained may provide future benefits for individuals with PTSD in improving understanding of PTSD treatments, and may improve future treatments.

Compensation and/or Reimbursement

Will compensation or reimbursement for expenses be offered to subjects?

Yes

Please describe and indicate total amount and schedule of payment(s).

Include justification for compensation amounts and indicate if there are bonus payments.

All subjects will receive \$100 for each evaluation visit (Baseline, Week 4, End of treatment, and Follow-up). Compensation will be mailed to the subject in the form of a check within 6 weeks of the completion of the baseline, week 4, end of treatment, and three month follow-up. Patients participating in the MRI scans will be compensated \$175 for each scan. At the final treatment sessions, participants will also be given the boots worn during the study. Participants will be compensated up to a total of 400\$ for participation in the study if they complete all evaluations. If participants are eligible for MRIs they would be compensated up to 750\$ (400\$ for assessments, 350\$ for both MRIs) for their participation in the study.

References

References

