Cover Page for ClinicalTrials.gov

Official Title of the Study:

Trauma-Focused Equine-Assisted Therapy (TF-EAT) for Veterans With PTSD

NCT Number:

NCT03068325

Principal Investigator:

[name]

[contact]

[contact]

Date of Document:

February 9, 2022

Statistical Analysis Plan

The Little MCAR (missing completely at random) test on total scores for the CAPS-5, PCL-5, HDRS, and BDI-II from each time point following the baseline assessment (i.e., midpoint, posttreatment, and follow-up analysis) will be used to test whether data is missing at random.

In line with previous open-trial studies exploring novel psychotherapies for different psychopathologies, we will use an intent-to-treat analysis, thereby enabling data analysis for all 63 patients. Provided that missing data is minimal and missing at random, we will conduct the intent-to-treat analysis with full information maximum likelihood (FIML), a gold standard approach to handling missing data. In addition, we will repeat analyses for patients who complete assessments at all four time points. Treatment effects will be explored using a repeated-measures analysis of variance (ANOVA) with time (pretreatment, midpoint, posttreatment, and follow-up) as a within-subjects factor. Post hoc tests using the Bonferroni correction will be used to compare the different time points. All statistical tests will be 2-sided, using $\alpha \leq .05$. Effect sizes will be reported using η^2 and Cohen d when appropriate.

Protocol Title: **Trauma-Focused Equine-Assisted Treatment (TF-EAT) for Veterans with PTSD**

Version Date:
02/09/2022

Protocol Number:
7232

First Approval:
03/11/2016

Expiration Date:
02/21/2023

Contact Principal Investigator:
[name], PHD
Email: [contact]
[contact]

Co-Investigator(s):
[name]
[name], PHD

Research Chief:
[name]

Cover Sheet

Choose **ONE** option from the following that is applicable to your study
If you are creating a new protocol, select "I am submitting a new protocol." As 5 Year Renewals are no longer required, this option remains for historical purposes.
I am submitting an annual continuation without modifications

Department & Unaffiliated Personnel

Department

What Department does the PI belong to?
Clinical Therapeutics
Within the department, what Center or group are you affiliated with, if any?
Anxiety Disorders Clinic

Unaffiliated Personnel

List investigators, if any, who will be participating in this protocol but are not affiliated with New York

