Feedback will be gathered from participants through two methods. First, two self-report questionnaires, the Client Satisfaction Questionnaire (CSQ-8) and the Credibility/ Expectancy Questionnaire, will be administered during treatment sessions 1, 4, and 8 to ascertain whether participants feel the treatment meets their needs and if they believe it is helping to alleviate their symptoms. Second, upon completing the treatment, a researcher will interview participants to gather feedback on their overall experience in the treatment. These interviews will be audiotaped and used in combination with the CSQ-8 and Credibility/Expectancy Questionnaire to inform modifications to the treatment. Staff members will also interview therapists post treatment to gather feedback on their perceived efficacy of the intervention. These interviews will also be audiotaped and used to inform decisions on modifying the intervention.

4.A.5. Therapists and adherence to protocol:

For equine therapy, Therapists (MD or PhD level, or Masters level for social workers) will be trained and supervised weekly, by Drs. [name], [name], and [name] (consultant). Horse handlers will be trained and supervised by [name]. [name] is an equine expert with significant experience in developing EAT exercises and training horses for use in EAT. Drs. [name] will view videotapes of sessions and midway through the project make a quarterly farm visit in person to ensure adherence.

4.A.6. Termination Procedures

Drs [name], Fisher and [name], in consultation with treating clinicians, will review all currently enrolled patients in treatment in a weekly meeting. Patients may be removed from the study upon:

1. Requests to withdraw from the study.
2. Elevated level of distress, for PTSD patients demonstrated by a score of 6 or higher on the weekly CGI for two consecutive weeks, unless the distress is due to an acute transient event (to be evaluated by treating clinician, and the PI). The CGI will be administered to consider both PTSD and Depression symptomatology.
3. Non-improvement in PTSD at week 4, as measured by the CGI-I at the level of 4 (no improvement) or higher.
4. Significant suicidal ideation, as assessed by the clinician and/or by the HAM-D-Item 3 and/or the BDI suicide item and/or the CVC Suicide Risk Assessment and Screener.
5. Clear-cut deterioration in social or occupational functioning as assessed by the clinician.

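### The FIML analysis names no auxiliary variables although week-4 CGI-I is a ground for removal; under certain conditions it can overstate improvement slightly (0 to about 0.09 SD)

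*Combined protocol and SAP*

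**What the plan says.** **Missingness check (SAP).** The plan applies "The Little MCAR (missing completely at random) test on total scores for the CAPS-5, PCL-5, HDRS, and BDI-II", with scores taken "from each time point following the baseline assessment (i.e., midpoint, posttreatment, and follow-up analysis". Baseline totals are not in the test.

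**Main analysis (SAP).** "Provided that missing data is minimal and missing at random, we will conduct the intent-to-treat analysis with full information maximum likelihood (FIML"). The model has "time (pretreatment, midpoint, posttreatment, and follow-up) as a within-subjects factor", so each outcome's pretreatment and midpoint scores enter the likelihood. No auxiliary variable is named. The only second analysis is in completers: "we will repeat analyses for patients who complete assessments at all four time points".

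**Removal (protocol, 4.A.6 Termination Procedures).** One ground is "Non-improvement in PTSD at week 4, as measured by the CGI-I at the level of 4 (no improvement) or higher". This section makes removal permissive. Item 7 under Other Procedures for Minimizing Risk words discharge for failure to benefit as something that will happen. The two places must be reconciled. Neither says whether a removed patient is still assessed at posttreatment and follow-up.

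**Availability of CGI (protocol, Flow Chart of Study Procedures and Table 1).** The independent evaluator rates the CGI between treatment visits 4 and 5, in the same session as the CAPS-5 and HAM-D. Table 1 lists both a severity and a change rating; I take the change rating to be the CGI-I.

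**The concern.** FIML corrects for selective loss only through variables that are in the model. Here the protocol itself names a variable that can cause loss, and the SAP does not say it will be used. Patients removed as non-improvers would have their later scores predicted from their baseline and midpoint totals alone. If, at equal totals, patients with a poor CGI-I go on to do worse, those predictions are too favourable.

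The trial has one arm, so within-patient change is the efficacy estimate and no control group offsets such an error. The completer analysis is no safeguard, because removal of non-improvers pushes it the same way, and further.

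**Working it through.** **1. Figures in the documents.** Intent-to-treat sample: 71 enrolled − 8 pilot = 63, which reproduces the SAP. Non-completion (Overall Progress): 71 − 64 = 7; 7/71 = 9.9%, or 7/63 = 11.1% if all seven were in the trial phase. Planned loss (Description of Subject Population): (70 − 60)/70 = 14.3%.

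**2. Assumed inputs.** The documents give no SDs, correlations or expected change. I take SD 1 at each visit; correlations 0.6 baseline–midpoint, 0.5 baseline–posttreatment, 0.75 midpoint–posttreatment; and a true change of −1 SD. A continuous CGI-I correlates 0.5 or 0.7 with change to midpoint, and q = 0, 0.2 or 0.4 with the posttreatment residual (what baseline and midpoint scores leave unexplained). The worst fraction f on CGI-I is removed and not assessed again.

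**3. Size by hand.** Share of posttreatment variance explained by the two earlier scores:

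R² = (0.5² + 0.75² − 2 × 0.5 × 0.75 × 0.6)/(1 − 0.6²) = 0.3625/0.64 = 0.566, so the residual SD is √(1 − 0.566) = 0.658.

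Mean residual among retained patients = −q × 0.658 × φ(z)/(1 − f), where z is the normal cut-off for f.

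- f = 9.9%, q = 0.4: 0.4 × 0.658 × 0.174/0.901 = 0.051 SD
- f = 14.3%, q = 0.4: 0.4 × 0.658 × 0.226/0.857 = 0.069 SD
- q = 0: 0 for any f

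This is slightly low, because FIML also extrapolates to the removed patients from a regression fitted in the retained ones.

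**4. Size by simulation** (unstructured covariance, very large samples). Overstatement of improvement in SD; ranges cover the two CGI-I correlations with early change, and the completer column also covers all three q.

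| Removed | FIML, q = 0 | FIML, q = 0.2 | FIML, q = 0.4 | Completers |
|---|---|---|---|---|
| 9.9% | 0.00 | 0.028–0.030 | 0.055–0.060 | 0.07–0.15 |
| 11.1% | 0.00 | 0.030–0.033 | 0.061–0.066 | 0.08–0.16 |
| 14.3% | 0.00 | 0.038–0.042 | 0.076–0.084 | 0.10–0.20 |

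A second simulation with similar inputs reached about 0.09 SD. With CGI-I as an auxiliary variable the FIML error is about 0 throughout.

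For scale, the SD of change is √(2 × (1 − 0.5)) = 1.0, so its standard error with 63 patients is 1.0/√63 = 0.126 SD. The top of the range, 0.09, is 0.09/0.126 = 0.71 of a standard error; the 9.9% row reaches at most 0.060/0.126 = 0.48.

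**5. Little's test** (63 patients, four scales, 400 runs per setting, 5% level; assumed mechanisms).

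| Loss | Rejects as planned | Rejects with baseline added |
|---|---|---|
| 7 or 9 removed at week 4 on lack of improvement | 13–14% | 44–51% |
| 7 or 9 lost before midpoint on high baseline | 0% | 65–73% |
| 7 or 9 lost at random | about 6% | 5–6% |

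The zero follows from the construction: a patient lost before midpoint has no score in the planned test.

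**6. Does baseline-driven loss bias the estimate?** No. With 15% lost before midpoint because of high baseline scores, FIML bias is 0.00 SD, since the pretreatment score is in the model. The completer estimate errs in the opposite direction, understating improvement by about 0.09 SD (0.13 SD at 16% loss with stronger dependence).

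**The case against.** The case against runs as follows. FIML already conditions on baseline and midpoint scores. The midpoint CAPS-5 is rated in the same session as the CGI and should carry much of the same information, so q may be near zero and the bias with it. The documents do not show that anyone was removed under this rule: the seven non-completers cover all reasons and may include pilot patients. The 10% row therefore needs essentially every one of them to be a CGI-I removal. The SAP is silent on auxiliary variables rather than excluding them, and omitting them is not in itself an error. All of this stands, and it is why the finding is conditional and small. It does not remove the case for naming a variable that the protocol itself makes a cause of loss.

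A reader might go further and infer that leaving baseline out of Little's test hides selective loss and so biases the result. The blindness to early loss is real, but the bias does not follow, as step 6 shows. For week-4 removal the test is weak, not blind, because midpoint scores are in it.

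Nor is adding baseline to the test a remedy by itself. The SAP uses FIML "Provided that missing data is minimal and missing at random", and the check offered for this is a test of missing completely at random. Adding baseline would make that test reject more often in exactly the settings where loss depends on scores that FIML models. A valid analysis would be blocked, leaving the completer analysis as the only other one named.

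**Conclusion.** The SAP should name the week-4 CGI ratings as auxiliary variables; that is a worthwhile refinement, not the repair of a demonstrated error. Overstatement needs three things together: removals on CGI-I, no assessment afterwards, and prediction of later outcome by CGI-I beyond the baseline and midpoint scores. Under the assumed correlations and 10 to 14% removal it is 0 to about 0.09 SD of an assumed 1 SD change, less than one standard error.

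A reader might conclude that improvement in this trial is overstated. The documents do not support that: they give no reasons for the seven losses. The negative answer on investigator withdrawals sits in the current-year summary, a year with no new consents, so it does not settle the matter either way.

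Little's test as planned is a poor detector, but its blindness to baseline-driven loss does not bias FIML.

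**What to change.** 1. In the FIML model for each scale, include week-4 CGI-I and CGI-S as auxiliary variables, and state which rater's CGI is used.
2. Tabulate baseline scores and week-4 CGI-I for patients with and without posttreatment data, with reasons for loss. This shows whether the rule removed anyone.
3. Baseline scores may be added to the missingness check as description. State that its result does not decide whether FIML is used.
4. Reconcile the two passages on removal for lack of benefit, and state whether removed patients were still assessed.

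The cost is SAP wording, a few lines of code and one table. No new data are needed. Two auxiliary variables raise the covariance terms per scale from 4 × 5/2 = 10 to 6 × 7/2 = 21, which is workable with 63 patients. The continuation form reports that only analysis remains and that a paper on the open trial has appeared, so results under this change should be labelled as added after data collection.

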6. Non-compliance with protocol requirements.
7. New or inter-current illness that prevents the patient from complying with the protocol.

Upon termination from this study, patients may be offered alternative treatment within the Columbia Veterans Research Center (IRB #7218). Patients removed from treatment due to elevated suicide risk will be assessed by Columbia Veterans Research Center MD/PhD clinicians and provided with immediate assistance as appropriate.

You can upload charts or diagrams if any

Blood and other Biological Samples

Please create or insert a table describing the proposed collection of blood or other biological specimens
All labs will be collected under the screening protocol (IRB #7094R). A urine sample will be collected for pregnancy tests at the initial evaluation and prior to the MRI scans for female participants.

Assessment Instruments

Create a table or give a brief description of the instruments that will be used for assessment
SCID (90 minutes at screening)

Beck Depression Inventory (10 minutes)

Clinical Global Impression – Severity Scale (CGI-S) (5 minutes)

Clinical Global Impression – Change Scale (CGI-S) (5 minutes)

Clinician Administered PTSD Scale (CAPS-4) (30 Minutes)

Clinician Administered PTSD Scale (CAPS-5) (30 Minutes)

PTSD Checklist (PCL-5)

Hamilton Rating Scale for Depression (Ham-D 17) (10 minutes)

Mini Mental State Exam (MMSE)

Quality of Life (SF-12) (10 minutes)

Family Assessment Device (FAD) (15 minutes)

Client Satisfaction Questionnaire (CSQ-18/CSQ-8)

Credibility/Expectancy Questionnaire

M2C-Q

Life Events Checklist (LEC-5)

POMS

Q-LES-Q-SF

SAS

Childhood Trauma Questionnaire (CTQ) (5 minutes)

CAGE-AID Questionnaire (CAGE-AID) (5 minutes)

Columbia Veterans Center Background Information Questionnaire (5 minutes)

Columbia Veterans Center Suicide Risk Assessment and Screener (10 minutes)

Deployment Risk and Resilience Inventory (DRRI-2) (20 minutes)

Generalized Anxiety Disorder 7-Item (GAD-7) (5 minutes)

VA Traumatic Brain Injury Screening Tool (VATBIST) (5 minutes)

Anxiety Disorders Clinic Demographic and Clinical Information (5 minutes)

Traumatic Brain Injury Identification Method (TBI ID) 5 minutes

Clinician Administered Patient Treatment Log (5 minutes)

Please attach copies, unless standard instruments are used

Research Related Delay to Treatment

Will research procedures result in a delay to treatment?

Yes

Maximum duration of delay to any treatment

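### The SAP's only repeat analysis, in patients with all four assessments, can be selected on early response and so cannot support the FIML result against response-related removal

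*Combined protocol and SAP*

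**What the plan says.** The Statistical Analysis Plan sets FIML on all 63 patients as the intent-to-treat analysis, under the condition "Provided that missing data is minimal and missing at random". It then adds that "we will repeat analyses for patients who complete assessments at all four time points". It names no further sensitivity analysis and no fallback if the condition fails. A Little MCAR test is planned on CAPS-5, PCL-5, HDRS and BDI-II totals; CGI is not among them.

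Protocol section 4.A.6, Termination Procedures, has a weekly review in which study leaders, "in consultation with treating clinicians, will review all currently enrolled patients in treatment in a weekly meeting". The list of grounds opens with "Patients may be removed from the study upon". Criterion 2 is "a score of 6 or higher on the weekly CGI for two consecutive weeks", unless the distress is transient. Criterion 3 is "Non-improvement in PTSD at week 4, as measured by the CGI-I at the level of 4 (no improvement) or higher". Criterion 5 is deterioration in functioning. Item 7 under Other Procedures for Minimizing Risk is worded more firmly: "Patients failing to benefit from the study treatment will be discharged from the study".

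On what follows removal, section 4.A.6 says only: "Upon termination from this study, patients may be offered alternative treatment within the Columbia Veterans Research Center".

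**The concern.** Several removal grounds are defined by poor response. If removal ends study assessments, a patient removed at week 4 has no post-treatment or follow-up score and leaves the four-assessment set. What remains leans toward responders, and in a single-arm study no control group shares that lean. At stake is mainly the reported effect size (Cohen d).

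The repeat also cannot do what a reader may expect of it. A complete-case analysis is valid under narrower conditions than FIML.

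- If removal follows recorded week-4 scores, FIML handles it, and a gap between the analyses shows only the completers' own selection.
- If removal also follows information outside the model, both analyses lean toward benefit, and agreement is no reassurance.

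**Working it through.** **Inputs from the documents.** Summary of Experiences to Date: 71 enrolled, 8 pilot and 63 trial. Overall Progress: 64 completed, with no definition, split by phase or reasons. Description of Subject Population: 60 completers from 70 enrolled. Flow Chart of Study Procedures: CAPS-5, HAM-D 17 and CGI are rated together between treatment visits 4 and 5.

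**Assumed, because the documents give no SDs or correlations.** Change scores are scaled to SD 1. rho, the correlation of the removal rating with later change, is 0.3 to 0.7.

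**1. The plan's own count.** 71 − 8 = 63, which reproduces the SAP figure.

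**2. How many can be missing.** Non-completers: 71 − 64 = 7, or 7/71 = 9.9%. The plan allowed 10/70 = 14.3%. If all 7 were trial patients, 63 − 7 = 56 remain and 7/63 = 11.1% are missing. If all 7 were pilot patients, none of the 63 is missing. This takes completed to mean all four assessments; if it means less, the four-assessment set could be smaller than 56.

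**3. Shift in the completer mean.** If the k patients lowest on the removal rating are lost, with p = k/63, completer mean change is overstated by rho × φ(z_p)/(1 − p).

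| k removed for non-benefit | p | φ(z_p) | φ(z_p)/(1 − p) | rho 0.3 | rho 0.5 | rho 0.7 |
|---|---|---|---|---|---|---|
| 0 | 0 | – | 0 | 0 | 0 | 0 |
| 3 | 0.048 | 0.0992 | 0.104 | 0.031 | 0.052 | 0.073 |
| 7 | 0.111 | 0.1894 | 0.213 | 0.064 | 0.107 | 0.149 |

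For comparison, the standard error of the completer mean change is 1/√56 = 0.134 SD.

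**4. What happens to FIML.** Simulation with n = 63 and 7 removed on week-4 CGI-I, their week-8 change missing and week-4 change observed. Assumed correlations: week-4 with week-8 change 0.5 or 0.7; CGI-I with week-4 change 0.6 or 0.8.

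| CGI-I and week-8 change | Completer bias (SD) | FIML bias without CGI (SD) |
|---|---|---|
| CGI-I adds nothing beyond week-4 change | 0.06 to 0.12 | about 0 |
| Correlation 0.5 | 0.10 | −0.02 to 0.05 |
| Correlation 0.7 | 0.15 | 0.04 to 0.10 |

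The top FIML value (0.095) arises when CGI-I tracks week-8 change (0.7) more closely than week-4 change does (0.5).

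**5. Why agreement does not reassure.** In a separate simulation (outcome SD units, 7 removed), removal tied to the unobserved later course overstated improvement in both analyses: FIML by 0.08 to 0.14 SD, completers by 0.14 to 0.24 SD.

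**The case against.** **The SAP never calls the repeat a robustness check.** This is correct. A reader might infer that the plan rests its defence of FIML on the completers, but the text says only that analyses will be repeated. The point is that nothing else is planned that could serve.

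**No removal for non-benefit is documented.** Also correct. A reader might infer from the 7 non-completers that non-responders were taken out. The documents give no reasons, and section 4.A.6 also lists withdrawal requests, suicidal ideation, non-compliance and illness. The protocol reports no significant departure from expected retention. Its negative answer on investigator withdrawals falls under a current-year heading, in a year with no new consents and with interventions complete, so it does not settle earlier years.

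**Loss of data after removal is inferred.** The section on minimizing risks schedules HAM-D 17 and BDI-II for all participants at week 8 and follow-up. It does not say whether removed patients are included, and that statement does not cover CAPS-5 or PCL-5. The inference is likely but not certain.

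**Seven removed is a stacked case.** It needs all seven to be trial patients, all removed for non-benefit, and all lowest on the rating. It stands only as an upper case.

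**The SAP already tests missingness.** The Little test examines MCAR on outcome totals without CGI. It cannot establish missing at random or detect removal on unmodelled information.

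**Adding CGI may gain nothing.** That is so if CGI-I carries nothing beyond the week-4 scores. The cost in precision is then also negligible, at most about 0.003 SD on the standard error.

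**Conclusion.** The point holds in a modest, conditional form. The four-assessment repeat can be selected on early response and relies on a stronger assumption than FIML, so it cannot support the FIML result against response-related removal.

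The completer overstatement is 0 if nobody was removed for non-benefit, and about 0.06 to 0.15 SD in the upper case of 7 of 63. That range rests on the assumed correlations of 0.3 to 0.7 and on reading completed as all four assessments.

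A reader might go further and conclude that the main analysis is biased. The documents do not support that. For removals at or after week 4, midpoint outcome scores are available to FIML, and its bias is near zero unless CGI-I predicts later change beyond those scores, when it could reach about 0.10 SD. The SAP does not list the FIML model's variables, so whether CGI is already included is unknown. Removal before week 4, which criterion 2 allows, would not have this protection.

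This is a cheap improvement, not a flaw that overturns the plan.

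**What to change.** **(a)** Include week-4 CGI-I and CGI-S, which the protocol already schedules, as auxiliary variables in the FIML analysis of all 63. This does not help patients removed before week 4; for them, use the weekly CGI ratings in criterion 2 if recorded.

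**(b)** Count removals by reason and time. If any were for non-benefit or deterioration, add one sensitivity analysis on all 63 that multiply imputes those patients with no further improvement after removal, and use return to pretreatment level as a harsher bound. Report the completer result as descriptive only. If there were none, say so and skip this step.

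Label both as post hoc: interventions are complete and the open-trial paper is published. They apply to whatever analyses remain.

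Separately, section 4.A.6 (removal permitted) and item 7 under Other Procedures for Minimizing Risk (discharge stated as certain) must be reconciled. The point holds under either.

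**Cost.** At most two extra runs on collected data, a few lines of text, and possibly a slightly smaller effect. The mean change falls by (k/63) × the gain no longer credited:

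- No further improvement, assumed later gain 0.3 to 0.5 SD: 3/63 gives 0.014 to 0.024 SD; 7/63 gives 0.033 to 0.056 SD.
- Return to pretreatment level, assumed total gain 0.5 to 1.0 SD: 7/63 gives 0.056 to 0.111 SD.
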